## **Objectives**

To investigate the sleep of the adult orthodontic patient population at the Case Western Reserve University School of Dental Medicine using the NOSE Questionnaire, STOP-Bang Questionnaire, Epworth Sleepiness Scale, Insomnia Severity Index, PROMIS Sleep Disturbance Questionnaire, Sleep Cycle app, and Belun Ring.

## **Experimental design**

The project will be a descriptive cross-sectional study.

A total of 55 adult participants will be recruited from the Case Western Reserve Orthodontics Clinic, based on the sample size calculation with a power of 80%. Inclusion criteria: current adult patients in the Case Western Reserve Orthodontics Clinic, ages 20-75, willingness to give informed consent

and participate in study, owner of a smartphone, and ability to return the Belun Ring and complete follow-up questionnaire. Exclusion criteria: age <20, currently or with history of taking blood pressure medication, currently undergoing transverse or anterior-posterior orthodontic correction, and currently pregnant or trying to become pregnant.

Participants will provide informed consent and will be instructed on the steps of the study. Demographic information will be collected, including a participant identifier, age of participant, and sex of participant. The use of the Belun Ring will be demonstrated, and they will be instructed on use of the Sleep Cycle app. They will complete the NOSE Score Questionnaire, STOP-Bang Questionnaire, Insomnia Severity Index, PROMIS Sleep Disturbance Questionnaire, and the Epworth Sleepiness Scale (ESS).

Data collected from the STOP-Bang Questionnaire includes positive/negative responses to: snoring, tired, observed, pressure, BMI >35, age over 50, neck size large, male gender, and the resulting OSA risk assessment of low, intermediate, or high.

Data collected from the NOSE Questionnaire includes positive or negative responses to: nasal congestion or stuffiness, nasal blockage or obstruction, trouble breathing through my nose, trouble sleeping, unable to get enough air through my nose during exercise or exertion, and the resulting classification of severity of nasal obstruction (mild, moderate, severe, extreme).

Data collected from the Insomnia Severity Index include difficulty falling or staying asleep, problem with waking up too early, satisfaction level with current sleep pattern, noticeability of subject's sleep problem to others, and amount of distress regarding current sleep habits.

Data collected from the PROMIS Sleep Disturbance Questionnaire includes level of agreement with statements about the subject's ability to fall asleep, quality of sleep, amount of sleep, level of satisfaction with their sleep, ability to stay asleep throughout the night.

The Epworth Sleepiness Scale collects information regarding the subject's likelihood of falling asleep during the following activities: sitting and reading, watching television, sitting in public, sitting in a car, lying down to rest, sitting and talking to someone, sitting quietly after lunch without alcohol, and while sitting in a car stopped in traffic.

The participants are then instructed to wear the Belun Ring for seven nights and simultaneously use the Sleep Cycle app.

Data collected from the Belun Ring includes the Respiratory Event Index (REI) (derived from total sleep time, heart rate variability, and O2 saturation changes), Sleep Efficiency (time participant is asleep divided by total time in bed), stress level, mean spO2 (%), Sleep Score (bAHI, Belun Ring's version of AHI), REM sleep (percentage), minimum spO2 (%), mean pulse rate (bpm), percent of time below 90% oxygen saturation, and total sleep time (minutes).

The Sleep Cycle app will collect the subject's time asleep, stages "Awake, Sleep, and Deep Sleep," sleep regularity, time to bed, time woken up, time in bed, sleep efficiency, heart rate, and time snoring. It also will record audio while the subject is asleep. During the night, the subject's

smartphone will be placed on their nightstand. The subjects also have the option to add “sleep notes” to give additional information about their night of sleep, for example, if they were feeling sick or if they exercised right before bed.

The subjects will return to the Case Western Reserve Orthodontic Clinic for their next orthodontic adjustment appointment. The subjects will return the Belun Ring to the clinic and we will download the data. The Sleep Cycle Score Report from each night will be collected by either sharing via WhatsApp, an encrypted messaging service, or recording the data points manually into an Excel spreadsheet.

Subjects will then complete a Follow-Up Questionnaire. They will record the dates they used the devices during sleep. Subjects will also indicate whether they had a “normal” night of sleep, or if they were experiencing sickness, allergies, or any other sleep disruptions that may have affected the data collected. They will also indicate whether they have a bed partner.

Participants will be referred for further evaluation, if needed.

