## **Evaluating the Sleep of an Orthodontic Population Using Emerging Technologies**

Sleep disordered breathing is a highly prevalent indication of airflow limitation. Airflow limitations can occur at the level of the nasopharynx, oropharynx, or hypopharynx. Sleep disordered breathing has a multifactorial etiology, including large fat deposits, a large tongue, consumption of alcohol or sedatives, illness, or excessive relaxation of pharyngeal musculature, among others. These airflow limitations can cause daytime sleepiness, a decrease in productivity, increased blood pressure, or automobile accidents.

Severe airflow limitations can be categorized as either apneas or hypopneas. An apnea involves total breathing cessation for over 10 seconds. A hypopnea involves a partial blockage of airflow for over 10 seconds. These events can culminate in arousal from sleep and gasping for air. The Apnea Hypopnea Index (AHI) is the number of events that occur per hour.

A diagnosis of obstructive sleep apnea involves an AHI score of at least 5. Sleep apnea diagnosis is separated into three categories: mild, moderate, or severe. Mild sleep apnea consists of an AHI score of 5-15 events per hour. Moderate sleep apnea consists of an AHI score of 15-30 events per hour. Severe sleep apnea has an AHI score of over 30 events per hour.

Risk factors for sleep disordered breathing include the male sex, age over 50, BMI >35, a large neck circumference, nasal congestion, diabetes, family history of OSA, and smoking.

Obstructive sleep apnea is highly prevalent, as an estimated 29.4 million adults in the United States have obstructive sleep apnea, though 23.5 million are undiagnosed. This points to the importance of accurate screening tools.

Sleep apnea can be treated using Continuous Positive Airway Pressure (CPAP), oral appliances such as mandibular advancement devices, a hypoglossal nerve stimulation device, lifestyle changes, or surgical intervention such as maxillomandibular advancement, removal of palatine tonsils/adenoids, tongue reduction surgery, or septoplasty.

Untreated sleep disordered breathing can cause many negative effects, including weight gain, cognitive impairment, memory loss, and increased daytime sleepiness. It can also lead to an increased risk of comorbidities, including hypertension, atrial fibrillation, heart attack, stroke, Type 2 diabetes, and depression.

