### **Statistical Analysis Design**

Out of the seven nights of sleep studied, the five with the longest night of sleep will be used for analysis. The values from those five nights will be averaged for each patient.

Descriptive statistics will be applied to the data, in order to determine reliability and consistency among different data collection methods, since similar variables are collected by different means. Correlation of data collected by different methods will be performed in order to cross examine and further validate results.

We will compare the accuracy of the response to the STOP-Bang question “Do you snore?” to audio data from the Sleep Cycle app. We will also compare the amount of snoring reported to the nasal obstruction score of the NOSE questionnaire. We will compare the distribution of the STOP-Bang questionnaire results (low/medium/high risk of Obstructive Sleep Apnea) to the distribution of results from the sensors. We will compare the agreement in recommendation for follow-up between the STOP-Bang Questionnaire and the sensors. Last, we will collect the percentage of people in the adult orthodontic clinic that should be referred for further evaluation for potential intervention.

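### Patients with diagnosed or treated sleep apnea can enrol and no described data item records it, so STOP-Bang/sensor agreement and the referral percentage can mix different kinds of participant

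*Combined protocol and SAP*

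**What the plan says.** All of this is in the combined protocol and SAP.

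- **Who can enter (Experimental design).** The inclusion list starts from "current adult patients in the Case Western Reserve Orthodontics Clinic, ages 20-75" and adds consent, a smartphone, and return of the ring with a follow-up questionnaire. The exclusion list reads "Exclusion criteria: age <20, currently or with history of taking blood pressure medication, currently undergoing transverse or anterior-posterior orthodontic correction, and currently pregnant or trying" (cut short within the pregnancy item, which is the last).
- **What is recorded (Experimental design).** "Demographic information will be collected, including a participant identifier, age of participant, and sex of participant". STOP-Bang contributes "positive/negative responses to: snoring, tired, observed, pressure, BMI >35, age over 50, neck size large, male gender". The NOSE, Insomnia Severity Index, PROMIS and Epworth forms ask about nasal symptoms, sleep and sleepiness. The Follow-Up Questionnaire is described as covering dates of device use, whether nights were normal or disturbed, and whether there is a bed partner.
- **What treatments exist (background).** "Sleep apnea can be treated using Continuous Positive Airway Pressure (CPAP), oral appliances such as mandibular advancement devices"; nerve stimulation, lifestyle change and surgery are also named.
- **What is analysed (Statistical Analysis Design).** The STOP-Bang risk distribution is set against the sensor distribution. Then: "We will compare the agreement in recommendation for follow-up between the STOP-Bang Questionnaire and the sensors". Last, the plan reports the percentage of the adult clinic to be referred for further evaluation.

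**The concern.** STOP-Bang and the ring respond differently to treatment. Age, sex, BMI and neck size do not depend on whether therapy is used on a given night. The ring's event index measures breathing as it is that night, with whatever therapy is in place. If therapy normalises the ring result while the fixed items keep STOP-Bang raised, the pair is recorded as a disagreement that says nothing about how well either tool screens.

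The referral percentage has a related problem. A person whose sleep apnea is already known and a person in whom it has gone undetected mean different things to a reader, and the plan cannot tell them apart. The background stresses undiagnosed disease, so readers will want that distinction.

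**Working it through.** **Step 1: is the status captured anywhere?** Going through every described item:

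| Source | Asks about sleep apnea diagnosis or treatment? |
|---|---|
| Inclusion and exclusion lists | No |
| Demographics (identifier, age, sex) | No |
| STOP-Bang, NOSE, ISI, PROMIS, Epworth | No |
| Follow-Up Questionnaire, as described | No; other sleep disruptions could bring it up by chance |
| Optional app sleep notes | Only if volunteered |

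The plan also does not say whether participants sleep with or without their usual therapy on study nights.

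**Step 2: can the disagreement arise?** STOP-Bang scores one point per positive item, and 3 or 4 is intermediate risk. A man over 50 with BMI above 35 and a neck above 40 cm scores 1 + 1 + 1 + 1 = 4 whatever he answers elsewhere. He is eligible if he has never taken blood pressure medication and meets the other criteria. If a score of 3 or more counts as positive (the plan does not say) and therapy gives him a normal ring result, he falls in the STOP-Bang-only cell.

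**Step 3: how many diagnosed participants?** The plan has no figure of its own to reproduce here. The background gives 29.4 million US adults with sleep apnea, 23.5 million of them undiagnosed.

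Diagnosed share = (29.4 − 23.5) / 29.4 = 5.9 / 29.4 = 20.1%.

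Expected number = 55 × prevalence × 0.201. Chance of at least one = 1 − (1 − prevalence × 0.201)^55. Clinic prevalence is not given, so it is an assumption:

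| Assumed prevalence | Expected diagnosed of 55 | Chance of at least one |
|---|---|---|
| 5% | 0.6 | 43% |
| 10% | 1.1 | 67% |
| 20% | 2.2 | 89% |
| 30% | 3.3 | 97% |

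These are diagnosed participants. The documents give no treated share.

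**Step 4: effect per participant.** Reclassifying one person moves raw agreement or the referral percentage by at most 1/55 = 1.8 points.

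**Step 5: effect on a chance-corrected measure (illustration only).** The plan names no agreement statistic, so Cohen's kappa is assumed, κ = (po − pe)/(1 − pe), with an invented table: 8 both positive, 6 STOP-Bang only, 5 sensor only, 36 neither.

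- As it stands: po = 44/55 = 0.800; pe = (14×13 + 41×42)/55² = 0.629; κ = 0.46.
- Therapy moves 1, 2 or 3 people from both positive to STOP-Bang only: raw agreement 78%, 76%, 75%; κ = 0.40, 0.33, 0.26.
- With two moved, leaving those two out of the comparison gives 6, 6, 5, 36 and κ = 0.39, against 0.33 with them in.

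For scale, the approximate standard error of κ in the starting table is √[po(1 − po)/(n(1 − pe)²)] = √[0.16/(55 × 0.371²)] ≈ 0.15.

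**The case against.** The strongest reply is that this is a descriptive study of a clinic population, and such a study should take all comers. The Objectives section sets out to investigate the sleep of that population, not to find new cases. That stands, and it is a good reason not to change eligibility. It does not remove the need to know who was measured under treatment.

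A reader might infer four stronger things, and the documents do not support them.

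- **That treated patients always push the comparison the same way.** Snoring, tiredness and observed apnea can change with treatment. A treated woman of 50 or under with BMI and neck size below the cut-offs can score 0 and be negative on both instruments. Someone with partial control, or not using therapy, can be positive on both. The plan also names no reference standard for this comparison, so a disagreement is not formally an error of the questionnaire.
- **That the referral percentage is inflated by 2 to 6 points as a measure of unmet need.** Statistical Analysis Design does not limit the figure to new or undiagnosed cases. Counts of 1.1 to 3.3 out of 55 are 2 to 6 points only if every known case is referred. No referral rule is given; if referral follows the ring, effective therapy lowers the percentage.
- **That the gap could never be repaired.** The demographics list is introduced as non-exhaustive, the full Follow-Up Questionnaire is not in the documents, and participants return to the clinic, so they could still be asked. The dataset as described would not hold the answer.
- **That anyone ever treated should be left out.** A person who has abandoned a device is measured untreated. What matters is therapy in effect on the study nights.

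It is also fair to say that the counts lean high. They apply a national share to one clinic. The exclusion for blood pressure medication probably removes some known cases too, since the background lists hypertension as a consequence of untreated disease.

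**Conclusion.** The gap is real and rests on the text alone: diagnosed or treated patients can enrol, no described item systematically records it, and the analysis section has no rule for them. Two outputs are exposed, the STOP-Bang/sensor comparison (distribution and agreement) and the referral percentage.

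The size is probably small: about 0.6 to 3.3 diagnosed participants among 55, if clinic prevalence is 5-30% and the 20% national diagnosed share applies, and likely fewer. Each is worth at most about 1.8 points on raw agreement or referral. The direction on the referral figure depends on the unstated rule. Kappa is more sensitive because positives are few; in the illustration, one to three people lower it by 0.06 to 0.20, against a standard error of about 0.15. That table is invented and shows sensitivity, not an expected result.

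This is a cheap improvement rather than a flaw that undermines the study.

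**What to change.** Keep the eligibility criteria as they are, and:

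1. Add one enrolment question: has the participant been diagnosed with sleep apnea, and have they had any treatment for it?
2. Add one Follow-Up Questionnaire question: was therapy in use on the study nights? That form already asks for dates, so it can be answered by night. This matters because the analysis averages the five longest of the seven nights.
3. State in Statistical Analysis Design that the STOP-Bang/sensor distribution and agreement comparisons will be run with and without participants measured under therapy. Say beforehand how therapy on only some of the five nights, and past airway surgery, will be classed.
4. Report the referral percentage separately for previously diagnosed and not previously diagnosed participants.

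The cost is two short questions, a few sentences in the analysis section, and up to about 3 participants fewer in the restricted comparisons. Everyone stays in the descriptive data.

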#### STOP-Bang Questionnaire

*Please answer the following questions by checking “yes” or “no” for each one*

	Yes	No
Snoring (Do you snore loudly?)		
Tiredness (Do you often feel tired, fatigued, or sleepy during the daytime?)		
Observed Apnea (Has anyone observed that you stop breathing, or choke or gasp during your sleep?)		
High Blood Pressure (Do you have or are you being treated for high blood pressure?)		
BMI (Is your body mass index more than 35 kg per m  ?)		
Age (Are you older than 50 years?)		
Neck Circumference (Is your neck circumference greater than 40 cm [15.75 inches]?)		
Gender (Are you male?)		

*Score 1 point for each positive response.*

*Scoring interpretation: 0 to 2 = low risk, 3 or 4 = intermediate risk, ≥ 5 = high risk.*

The NOSE Score Questionnaire involves a series of responses that yield a numerical score representative of the severity of nasal obstruction. The participant provides their responses to a variety of prompts using a ranking system from “Not a problem” (0 points) to “Severe problem” (4 points). The numerical responses are added, then the sum is multiplied by 5, to provide a result of “mild,” “moderate,” “severe,” or “extreme” nasal obstruction.

Over the past one month, how much of a problem were the following conditions for you?

	Not a problem	Very mild problem	Moderate problem	Fairly bad problem	Severe problem
Nasal congestion or stuffiness	0	1	2	3	4
Nasal blockage or obstruction	0	1	2	3	4
Trouble breathing through my nose	0	1	2	3	4
Trouble sleeping	0	1	2	3	4
Unable to get enough air through my nose during exercise or exertion	0	1	2	3	4

NOSE score (multiply your total score x5)

Nasal obstruction severity classification: mild (5-25) | moderate (30-50) | severe (55-75) | extreme (80-100)

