**LEVEL 2—Sleep Disturbance—Adult\***

\*PROMIS—Sleep Disturbance—Short Form

Name: \_\_\_\_\_ Age: \_\_\_\_\_ Sex:  Male  Female Date: \_\_\_\_\_

If the measure is being completed by an informant, what is your relationship with the individual receiving care? \_\_\_\_\_

In a typical week, approximately how much time do you spend with the individual receiving care? \_\_\_\_\_ hours/week

**Instructions to patient:** On the DSM-5 Level 1 cross-cutting questionnaire that you just completed, you indicated that *during the past 2 weeks* you (the individual receiving care) have been bothered by "problems with sleep that affected your sleep quality over all" at a mild or greater level of severity. The questions below ask about these feelings in more detail and especially how often you (the individual receiving care) have been bothered by a list of symptoms ***during the past 7 days***. Please respond to each item by marking (✓ or x) one box per row.

						Clinician Use
In the past SEVEN (7) DAYS....						
	Not at all	A little bit	Somewhat	Quite a bit	Very much	
1. My sleep was restless.	 1	 2	 3	 4	 5	
2. I was satisfied with my sleep.	 5	 4	 3	 2	 1	
3. My sleep was refreshing.	 5	 4	 3	 2	 1	
4. I had difficulty falling asleep.	 1	 2	 3	 4	 5	
In the past SEVEN (7) DAYS....						
	Never	Rarely	Sometimes	Often	Always	
5. I had trouble staying asleep.	 1	 2	 3	 4	 5	
6. I had trouble sleeping.	 1	 2	 3	 4	 5	
7. I got enough sleep.	 5	 4	 3	 2	 1	
In the past SEVEN (7) DAYS....						
	Very Poor	Poor	Fair	Good	Very good	

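### Would recording the NOSE items as positive or negative lose the score that the snoring comparison needs?

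*Combined protocol and SAP*

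**What the plan says.** The NOSE instrument is described and reproduced under the STOP-Bang Questionnaire heading of the combined protocol and SAP. Each of five items is graded from 0 to 4. On scoring, the text says "The numerical responses are added, then the sum is multiplied by 5". The form has its own score line, "NOSE score (multiply your total score x5", and prints the bands "Nasal obstruction severity classification: mild (5-25) | moderate (30-50) | severe (55-75) | extreme (80-100".

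The Experimental design section describes the same data differently: "Data collected from the NOSE Questionnaire includes positive or negative responses to: nasal congestion or stuffiness", then the other four items, and then "the resulting classification of severity of nasal obstruction (mild, moderate, severe, extreme". The paragraph just before it deals with the yes/no STOP-Bang form in nearly the same terms: "Data collected from the STOP-Bang Questionnaire includes positive/negative responses to: snoring".

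The Statistical Analysis Design section uses NOSE once: "We will also compare the amount of snoring reported to the nasal obstruction score of the NOSE questionnaire".

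A side point concerns another instrument. The preamble of the PROMIS form tells the participant "On the DSM-5 Level 1 cross-cutting questionnaire that you just completed, you indicated that" sleep had been a problem. The five questionnaires listed in the Experimental design section do not include a DSM-5 Level 1 form.

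**The concern.** The two descriptions of the NOSE items cannot both be right. No item on the printed form has a positive or negative answer, and the data list names neither the 0-4 grades nor the numeric total. The total is what the snoring comparison calls for. The documents contain no separate data dictionary for the questionnaires, so someone building the data sheet might work from this paragraph.

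In that case the file would hold five binary items and a four-level class. The comparison with snoring would then have to use the class, which is coarser than the score. The class also has no place for a participant without nasal complaints: a total of 0 lies below the lowest printed band, which starts at 5.

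The PROMIS preamble states something untrue for this study, which might in principle colour the answers.

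**Working it through.** **Inputs.** From the printed NOSE form: five items, each 0 to 4; score = 5 × sum of items; bands 5-25, 30-50, 55-75 and 80-100. From the Experimental design section: five binary items plus the class. That section gives no cut-off for a positive answer, so two are assumed below: a grade of 1 or more, and a grade of 2 or more.

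**Step 1: the form's own scale.** The maximum is 5 items × 4 points × 5 = 100, which matches the top of the highest band. Scores run from 0 to 100 in steps of 5, so there are 100/5 + 1 = 21 possible totals. Each of the four bands holds 5 of them (4 × 5 = 20). The one left over is 0.

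**Step 2: can the listed class come from binary items?** If the items were scored 0/1 under the same rule, the maximum would be 5 × 1 × 5 = 25. Only the mild band, or an unbanded 0, could be reached. The Experimental design sentence nevertheless names all four classes. Its class therefore presupposes the graded answers and their total, so the sentence cannot be describing an instrument answered only yes or no.

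**Step 3: what would be lost if only binaries and class were kept?** All 5^5 = 3125 answer patterns were enumerated and grouped by what such a file would hold: the positive/negative pattern plus the printed class, with the class blank for a total of 0.

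| Assumed meaning of positive | Distinct records | Total fixed exactly | Total not fixed | Possible totals when not fixed | Span (points) |
|---|---|---|---|---|---|
| Grade 1 or more | 80 | 7 | 73 | 2 to 5 | 5 to 20 |
| Grade 2 or more | 80 | 12 | 68 | 2 to 5 | 5 to 20 |

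At a cut-off of 1 or more, the seven fixed records are: no positives (total 0); five positives with mild (25); and four positives with extreme (80), which occurs in 5 patterns. 1 + 1 + 5 = 7.

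At 2 or more, the twelve are: no positives with a blank class (0); five positives with moderate (50); and two positives with severe (55), which occurs in 10 patterns. 1 + 1 + 10 = 12.

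These are counts of possible records. The records are not equally likely, so the counts are not proportions of the 55 participants and do not measure expected harm.

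**Step 4: what happens if the plan is followed?** The participant fills in the graded form. The five grades are on it, the score line is on it, and the class is read from the score. Entering either the grades or the score gives the 0-100 total, and the loss is zero. The Statistical Analysis Design section asks for the score, where 0 is an ordinary value, so a participant with no complaints is included in the comparison.

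**Step 5: is the data list meant to be complete?** Its treatment of the other questionnaires suggests not. For the Insomnia Severity Index it leaves out the item on interference with daily functioning and the 0-28 total. For PROMIS it leaves out the raw score and T-score, for STOP-Bang the numeric score, and for Epworth the total. A missing NOSE total is therefore weak evidence that the number will not be kept.

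**The case for a change.** The strongest case for acting is that the contradiction is real and cheap to remove. The data list is the only place in the documents that says which NOSE variables are captured, and it names the wrong type for a variable used in a planned comparison. The Statistical Analysis Design section does not say outright that the score means the 0-100 total. A total of 0 has no class however the data are entered, so any table by class needs a rule that the plan does not give. A few words would settle all of this at no cost to participants.

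The textual mismatch stands, and anyone tidying the document may correct it. The rest carries less weight:

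- The form labels its ×5 figure as the NOSE score, so the meaning of the score in the analysis section is not in real doubt.
- The zero-total gap is printed on the form and was not created by the data list. It affects only tabulation by class, where an analyst would show zeros as their own row.
- The damaging scenario needs staff to set aside the completed answers and to invent a cut-off. Nothing in the plan asks for either.

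The PROMIS preamble is standard text on a published form. It does not fit this study, but none of the named comparisons in the Statistical Analysis Design section uses PROMIS, and no effect on any result has been shown.

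**Conclusion.** This is a clerical slip, and the plan needs no change. The phrase describing NOSE answers as positive or negative is wrong for a 0-4 form and appears to repeat the wording used for STOP-Bang. The sentence that contains it also requires a class that only the graded total can supply, and the completed form carries both the grades and the score. Followed as written, the plan yields the 0-100 score for the snoring comparison with no loss.

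This conclusion assumes that the data are entered from the completed form. The documents include no data sheet, so that cannot be seen directly, but it is the natural reading. If the assumption failed, the comparison would fall back on four ordered classes with totals of 0 unplaced, and the exact total would be recoverable for only 7 or 12 of the 80 possible record types under the two assumed cut-offs. How to show a zero total in a table by class is a reporting detail that an analyst would settle. The PROMIS preamble is a separate, harmless mismatch of standard text.
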